## 8.4 Participant Withdrawal Criteria

Participants will be advised that they are free to withdraw from the study at any time for any reason or, if necessary, the PI, or medically trained designee, may withdraw a participant from the study, per the following criteria, to protect the participant's health:

- the need to take medication which may interfere with study measurements
- intolerable/unacceptable AEs
- major violation of or deviation from study protocol procedures
- non-compliance of participant with protocol
- participant unwilling to proceed and/or consent is withdrawn
- withdrawal of the participant from the study if, in the PI's judgement, it is in the participant's best interest
- confirmed pregnancy (Note: within 24 hours of awareness of the pregnancy the investigator must notify the Sponsor [see Section 11].)

The reasons for withdrawal will be recorded on the case report form (CRF) and included in the final clinical study report, along with any AEs and any necessary medical treatment.

If a participant is withdrawn from the study due to significant AE or SAE, the PI, or medically trained designee, will evaluate the urgency of the event. If the situation warrants, the PI, or medically trained designee, will take appropriate diagnostic and therapeutic measures. If the situation is not an immediate emergency, the PI, or medically trained designee, at the clinical study facility will attempt to contact the Arrowhead Pharmaceuticals, Inc. Medical Monitor or medically qualified designee for consultation. No medical help, diagnosis, or advice will be withheld from the participant due to an inability to contact the Medical Monitor. The participant will be encouraged to remain available for follow-up medical monitoring. The Sponsor will be notified as soon as possible of any participant withdrawals.

Participants who are withdrawn or discontinue prior to EOS visit for reasons other than an adverse event, may be replaced at Sponsor discretion.

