#### **Cohort Summary**

Cohort	Population	Blinding	# Subjects	Dosing Schedule
1	NHVs	Double blind	8 (4 active:	25 mg Day 1 only
			4 placebo)	
1b	Patients with suspected NASH	Open Label	up to 6	25 mg Days 1, 29
	(biopsies on screen and day 71)		(all active)	
2	NHVs	Double blind	8 (4 active:	50 mg Day 1 only
			4 placebo)	
3	NHVs	Double blind	8 (4 active:	≤ 100 mg Day 1 only
			4 placebo)	
4	NHVs	Double blind	8 (4 active:	$\leq$ 200 mg Day 1 only
			4 placebo)	
3b	Patients with suspected NASH	Open Label	up to 6	≤100 mg Days 1, 29
	(biopsies on screen and day 71)		(all active)	
4b	Patients with suspected NASH	Open Label	up to 6	≤200 mg Days 1, 29
	(biopsies on screen and day 71)		(all active)	

Approximately 50 subjects may be enrolled in the study (not including replacements or optional expansion cohort).

**Number of Doses per Treatment:** Single dose (Cohorts 1, 2, 3, 4) or two doses (Cohorts 1b, 3b and 4b) dosed 28 days apart

**Study Duration:** For subjects in Cohorts 1 through 4, the duration of the study clinic visits is approximately 158 days from screening to the End-of-Study visit. For subjects in Cohorts 1b, 3b and 4b, the duration of the study clinic visits is approximately up to 173 days from screening to the End-of-Study visit. Additionally, all subjects will have a 90-day post-end of study visit follow-up phone call assessing compliance with contraception.

**Study Confinement:** For all NHV cohorts (1-4), clinical facility confinement will be approximately 3 days for dose administration (Day -1 through 24-hour assessments) with discharge on Day 2. Subjects will return to the clinical facility for outpatient visits per the Schedule of Assessments. Patients in Cohorts 1b, 3b and 4b will be at the facility for approximately 4 hours (2 hours before dosing and 2 hours after dosing) on dosing days.

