# 11.3 Timing, Frequency, and Method of Detecting AEs

Any pre-existing conditions or signs and/or symptoms present in a participant prior to the start of the study (i.e., before informed consent) should be recorded as Medical/Surgical History.

All AEs occurring after informed consent and on or before the final visit must be reported as AEs; only AEs that occur post-dose will be considered treatment-emergent. All AEs must be recorded irrespective of whether they are considered drug-related. AEs will be collected through the EOS or through 30 days after the last dose whichever is longer.

At each visit/assessment in the period defined above, AEs will be evaluated by the PI (or medically qualified designee) and recorded.

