5. DEFINITIONS

Day 1:

For each subject, Day 1 is defined as the first day that protocol-specified study treatment is administered to the subject.

End of Study (EOS) Date:

For each subject, the EOS date is the study completion/early termination date recorded on the eCRF.

Study Day:

For each subject, and for a given date of interest, study day is defined as the number of days relative to Day 1:

- After first dose date: study day = date of interest – Day 1 date + 1
- Prior to first dose date: study day = date of interest – Day 1 date, so that the day prior to Day 1 is Day -1

Study End Date:

The study end date is when the last subject finishes the EOS visit.

Baseline Values:

For all variables, baseline is defined as the last non-missing value obtained prior to the first dose administration on Day 1.

For ECG, if a triplicate is taken prior to the first dose administered on Day 1, baseline is defined as the mean over the set of triplicate assessments.

Analysis Day:

Selected endpoints will be summarized based on Analysis Day defined using Study Day as below.

Scheduled Visit/ Analysis Day	Day 8	Day 15	Day 29	Day 43	Day 57	Day 71	Day 85	Day 99	Day 113
Study Day Window Cohort 1-4	[6,10]	[13,17]	[27,31]	[41, 45]	[55,59]	[69,73]	[83,87]	[97,101]	[111,115]
Study Day Window Cohort 1b,3b,4b	NA	[13,17]	[27,31]	NA	[55,59]	[66,76]	[83,87]	NA	[108,118]

If there is more than one record in a study day window, the analytical record for that specific analysis day will be defined as the record closest to the scheduled visit day. If two records are equidistant from the scheduled visit day, then the earlier record will be chosen. If there are multiple records on the same day, the last record will be used.

Duration of study:

EOS date – Day 1 date + 1

Treatment-Emergent Adverse Event (TEAE):

TEAEs are defined as adverse events occurring on or after the first dose of study treatment through EOS or pre-treatment existing conditions that worsen after the investigational product administration.

Treatment-emergent SAEs (TESAEs):

TESAEs are defined as serious adverse events occurring on or after the first dose of study treatment through EOS or pre-treatment existing conditions that worsen after the investigational product administration.

TEAE at Injection Site:

TEAE occur at the injection site. MedDRA Preferred Terms which are included in LISR are listed in Protocol Section 16.2.

TEAE Related to Local Injection Site Reaction (LISR):

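### Protocol 8.4 permits whole-study withdrawal of dosed participants for interfering medication, deviation or non-compliance, and names no option to stop study drug but stay in follow-up

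*Protocol*

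**What the plan says.** Protocol 8.4 states that the investigator or a medically trained designee, if necessary and to protect the participant's health, "may withdraw a participant from the study, per the following criteria". Three of the listed criteria are not in themselves safety events: "the need to take medication which may interfere with study measurements", "major violation of or deviation from study protocol procedures" and "non-compliance of participant with protocol". The section describes one outcome only, leaving the study. Its encouragement to stay available for monitoring sits in the paragraph on withdrawal for a significant AE or SAE. It closes with: "Participants who are withdrawn or discontinue prior to EOS visit for reasons other than an adverse event, may be replaced at Sponsor discretion".

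Dosing is short. The synopsis gives "Single dose (Cohorts 1, 2, 3, 4) or two doses (Cohorts 1b, 3b and 4b) dosed 28 days apart", so the last dose falls on Day 1 for volunteers and Day 29 for patients. End of study (EOS) is Day 113.

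On AE collection, Protocol 11.3 says "AEs will be collected through the EOS or through 30 days after the last dose whichever is longer". SAP section 5 counts treatment-emergent AEs from first dose through EOS and defines EOS as follows: "For each subject, the EOS date is the study completion/early termination date recorded on the eCRF".

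Elsewhere the documents do distinguish stopping drug from leaving the study. The stopping rules (synopsis and Protocol 7.4) mention discontinuing drug in an individual subject. Appendix 16.1 pairs drug interruption with close observation. SAP 9.2 reports treatment discontinuation and study discontinuation separately.

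**The concern.** The primary endpoint is the incidence and frequency of related AEs after dosing. Once a participant has had the last dose, removal from the study cannot reduce exposure, so what it takes away is observation. A withdrawn participant stays in the Safety Analysis Set, and so in the denominator, but has no further scheduled visit at which a new event would be sought. Protocol 11.9 adds that investigators need not actively seek AEs in former participants. Observed incidence can then only miss events. Starting a new medication or missing procedures may also follow from feeling unwell, in which case the loss would be informative.

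In the patient cohorts a second loss is possible. Protocol 5.6 treats liver biopsy as the sole means of measuring target silencing, and Table 2 schedules biopsy, MRI-PDFF and FibroScan at screening and Day 71 only. None of the three is marked in the EOS/Early Termination column.

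**Working it through.** **Inputs.** Screening opens at Day -45 (volunteers, Table 1) or Day -60 (patients, Table 2). EOS is Day 113 (Table 2; SAP section 5 for all cohorts). Last dose is Day 1 or Day 29. The AE collection floor is last dose + 30 days (Protocol 11.3). Each volunteer cohort has 4 active subjects, and each patient cohort has up to 6.

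**The plan's own figures.** 45 + 113 = 158 days and 60 + 113 = 173 days match the stated durations. 4 × 8 + 3 × 6 = 50 matches the stated enrolment. The timeline is therefore read correctly.

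**Follow-up at stake after the last dose (113 − last dosing day).**
- Volunteers: 113 − 1 = 112 days.
- Patients: 113 − 29 = 84 days.

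**What the 30-day floor protects.**
- Volunteers: to Day 1 + 30 = Day 31.
- Patients: to Day 29 + 30 = Day 59.

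**Days without scheduled collection of new AEs, for withdrawal on day w: 113 − max(w, floor day).** The maximum occurs when w is at or before the floor day.
- Volunteer: 113 − 31 = 82; 82/112 = 73%. As a share of a four-subject active group: 82/(4 × 112) = 18%.
- Patient: 113 − 59 = 54; 54/84 = 64%. As a share of a six-patient cohort: 54/(6 × 84) = 11%.

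**SAP window against Protocol 11.3.** If the recorded early termination date is day w, the SAP window for new events closes on w, while the protocol goes on collecting to the floor day. The mismatch is floor day − w.
- Volunteer with a Day 15 termination date: 31 − 15 = 16 days on which an AE is collected but falls outside the SAP's onset window.
- Patient terminating straight after the Day 29 dose: 59 − 29 = 30 days.

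The SAP's other limb, worsening of pre-treatment conditions, is not tied to EOS, so the mismatch concerns new events.

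**Biopsy.** Day 71 is 71 − 29 = 42 days after the last dose. One patient withdrawn in that interval is 1/6 = 17% of a full cohort's paired biopsy, MRI-PDFF and FibroScan data. The 95% t half-width for a mean change, t(0.975, n−1)/√n in SD units, goes from 1.05 (n = 6) to 1.24 (n = 5), an 18% increase.

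**Illustration for rare events (assumed true rates; one volunteer lost).** The chance of seeing at least one AE is 1 − (1 − p)^n. From 4 to 3 fully followed active subjects it falls:
- p = 10%: 34% to 27%
- p = 20%: 59% to 49%
- p = 30%: 76% to 66%

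This is an upper bound on the loss, because it treats the withdrawn subject as contributing nothing, whereas events up to withdrawal still count.

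**The case against.** The case on the other side is substantial.

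- **Discretion.** A reader might infer that 8.4 removes people automatically. It does not: the wording is permissive, and replacement is also at the sponsor's discretion. Protocol 8.5 lets the medical monitor and investigator approve concomitant medication, so a participant with a new prescription already has a route to stay. This stands.
- **Backstops.** A reader might infer that withdrawal ends safety follow-up altogether. It does not. There is an early termination visit with examination, ECG, laboratory tests and AE collection, as well as the 30-day floor. Existing AEs are followed to resolution or stability (11.6), and related SAEs are reportable after the study (11.9). This stands, and the figures above are net of the floor. None of these provisions replaces scheduled enquiry for new events to Day 113.
- **Bias not shown.** A reader might infer that related-AE incidence is understated. That follows only if a related event would have occurred after withdrawal. The documents do not show this, nor that losses would be informative.
- **Biopsy and replacement.** These are alternative consequences. If the patient is replaced, the biopsy count is restored. If not, nobody extra is exposed. Some interfering drugs may themselves preclude biopsy, since anticoagulants and antiplatelets appear in exclusion criterion 19. This also stands.
- **Scale.** The analysis is descriptive, with no hypotheses and no formal sample size, which limits the weight of the point.

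The gap in wording remains. Other sections recognise stopping drug as distinct from leaving the study, and 8.4 gives the investigator no such choice for these three reasons.

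**Conclusion.** The point holds as a weakness in a discretionary rule. For interfering medication, major deviation and non-compliance, 8.4 permits study withdrawal and names nothing short of it. After Day 1 (volunteers) or Day 29 (patients) that prevents no exposure. It can leave up to 73% of a volunteer's post-dose follow-up, or 64% of a patient's, without scheduled collection of new AEs. Separately, the SAP's EOS-based window can exclude from the primary-endpoint tables AEs that Protocol 11.3 requires to be collected. A patient lost between Day 29 and Day 71 costs 1 of 6 sets of Day 71 data in a full cohort unless replaced. Replacement exposes another patient to drug and biopsies without restoring the lost safety follow-up.

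The sizes assume EOS at Day 113, withdrawal at or before the floor day, and one participant lost. The documents give no withdrawal rate, so no expected total loss can be stated. Between Day 1 and Day 29, withdrawing a patient does remove the second dose. The argument that nothing is prevented does not apply to that interval.

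**What to change.** In Protocol 8.4:
- Separate discontinuation of study drug from withdrawal from the study.
- State that, for these three reasons, dosed participants are asked to remain in the scheduled safety assessments through EOS. In Cohorts 1b, 3b and 4b, they are also asked to attend the Day 71 assessments where consent and biopsy eligibility allow.
- Leave the consent-withdrawal, AE, best-interest and pregnancy grounds as they are. Leave every dosing decision, including the Day 29 dose, governed as it is now.
- Limit replacement to participants who have actually left follow-up.
- Flag the medication or deviation in the data.

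In SAP section 5, reconcile the end of the treatment-emergent window with the later-of rule in Protocol 11.3, so that AEs collected under that rule are counted.

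The cost is a wording amendment to both documents. No new visits are added, and concomitant medication is already recorded in the CRF. The downside is small: some retained pharmacodynamic values will have been taken on an interfering drug and need a flag or a sensitivity summary. Participants who stop attending cannot be kept by wording, so some loss will remain.

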### 8.5 Restrictions and Concomitant Medications

• *Confinement:* For all NHV cohorts, clinical facility confinement will be approximately 3 days for first dose administration (Day -1 through 24-hour assessments) with discharge on Day 2. Subjects will return to the clinical facility for outpatient visits per the Schedule

of Assessments. Patients in Cohorts 1b, 3b and 4b will be at the facility for approximately 4 hours (2 hours before dosing and 2 hours after dosing) on dosing days.

- *Fasting:* On the day of dosing or on other days with blood draws, participants will have fasted from food for at least 8 hours prior to study treatment administration or blood draw unless otherwise specified or as otherwise required by study procedures.
- Recreational Drugs & Alcohol: Participants will be instructed to abstain from consuming alcohol for at least 48 hours prior to admission, and while confined to the clinical facility. In addition, participants will be instructed to refrain from regular use of alcohol (i.e., >14 units per week or >4 units on a given day for men and >7 units per week or >3 units on a given day for women [1 Unit = 150 mL of wine, 360 mL of beer, or 45 mL of 40% alcohol]) for the study duration. Participants must abstain from use of recreational drugs throughout the study.
- *Concomitant Medications:* Use of other concomitant medications may be approved by sponsor medical monitor and PI. Patients will be instructed to inform the PI of the details (indication, dose and dates of administration) if they do take any medication, and these details will be recorded in the CRF. Medication wash-out to achieve study eligibility at screen constitutes a protocol procedure and will be preceded by informed consent.

#### 9. INVESTIGATIONAL PRODUCT

## 9.1 Description, Identification and Dosage

Arrowhead Pharmaceuticals, Inc. is responsible for the supply of active drug supplies together with detailed instructions (in a pharmacy manual) describing preparation of ARO-HSD. The PBO (normal saline 0.9%) will be supplied by the clinical site.

Accordingly, ARO-HSD will be supplied as single sterile 2-mL vials containing ARO-HSD, with the correct dose of ARO-HSD prepared by the Pharmacy prior to dosing participants.

The PBO will be 0.9% normal saline.

## Doses Administered per Dose Level:

Each single dose of either active drug (ARO-HSD) or PBO (normal saline 0.9%), will be administered by subcutaneous injection. Injections will be made into the subcutaneous tissue at an appropriate site (e.g. abdomen, thigh, upper arm, etc.) using a 25-30 Gauge, ½ inch needle. The abdomen is the preferred injection site. The injection site is to be varied (no multiple injections into the same exact site. Alternating various locations on the abdomen is acceptable). Injection site location is to be recorded in the eCRF. Prior to dose administration, the ARO-HSD vial must be allowed sufficient time to come to room temperature. Do not inject into areas of active skin disease or injury such as sunburns, skin rashes, inflammation or skin infections. Injection volume per site should not exceed approximately 1.0 mL.

There will be no dose escalation within a cohort (i.e., the same drug dose will be administered to each participant within a cohort). The randomization schedule for NHVs will be provided to each clinical site and will be maintained along with any other materials that could jeopardize the blind in a secured area of the pharmacy.

### Supply, Preparation, Storage, and Labelling of ARO-HSD

ARO-HSD will be supplied as a sterile Type-1 glass 2.0-mL vial (1.2 mL nominal volume, 1.0 mL withdrawable volume).

Strength: 200 mg/mL Volume: 1.0 mL

Appearance: Clear, colorless to yellow solution

Inactive ingredients: 0.5 mM sodium phosphate monobasic, 0.5 mM sodium

phosphate dibasic in water for injection

Shipment and storage: Refrigerated, 2-8 °C

ARO-HSD will be prepared, per the Pharmacy Manual, by a pharmacist or qualified pharmacy staff member at the clinical sites. Aseptic technique will be used to ensure sterility of the solution to be injected. The time of preparation for active drug must be documented and tracked to demonstrate administration within prepared drug stability boundaries. Please refer to the Pharmacy Manual for more detailed instructions.

The investigational product vials will be labelled per Good Manufacturing Practice (cGMP)/Good Clinical Practice (cGCP).

Study drug supplies will be stored at clinical sites securely under the appropriate conditions as noted in the Pharmacy Manual.

#### 9.2 **Study Drug Handling**

The Sponsor will provide the PI with a sufficient quantity of clinical drug supplies. The PI must ensure that deliveries of investigational product from the Sponsor are correctly received by a responsible person, that all receipts of drug shipments are recorded on the appropriate Drug Accountability forms prepared by the pharmacy at the clinical site and that the products are

stored in a secure area under recommended storage conditions. It is also the responsibility of the PI to ensure that the integrity of packaged study product not be jeopardized prior to dispensing.

Only participants enrolled in the study may receive study drug, in accordance with all applicable regulatory requirements. Only authorized site staff may supply or administer study drug. The study drug must be stored in a secure area with access limited to the PI and authorized staff and under the physical conditions that are consistent with the study drug-specific requirements.

An authorized and trained staff member at each clinical trial site will dispense the study drug per predefined drug dispensing requirements. The dispensing will be verified by a second member of site staff.

ARO-HSD will be supplied by Arrowhead Pharmaceuticals, Inc. and labelled with the drug name, batch number, expiration date (as applicable), and storage conditions. Individual doses will be dispensed by clinical trial site staff members on the morning of dosing and recorded in the drug accountability records. A Pharmacy Manual will be prepared to define the procedures for dispensing.

Procedures delineated in the Pharmacy Manual will be followed for the receipt, handling and accountability of the study formulations.

## 9.3 Accountability of Study Supplies

All study related material supplied is only for use in this clinical trial and should not be used for any other purpose. The PI is responsible for the investigational product accountability, reconciliation and record maintenance at the investigational site. In accordance with all applicable regulatory requirements, the PI or designated site staff must maintain investigational product accountability records throughout the course of the study. This person will document the amount of investigational product received from Arrowhead Pharmaceuticals, Inc. and the amount administered to participants. A non-blinded Clinical Research Associate (CRA) will perform initial and ongoing study drug kit and placebo accountability. The non-blinded CRA will protect the integrity of the assignment blind and will not participate in data review for study participants. Used vials of ARO-HSD will be retained sequestered per participant and cohort (where allowable by local policy) and made available to the non-blinded CRA during study drug and placebo reconciliation.

A Drug Dispensing Log must be kept current and will contain the following information:

- the identification of the participant to whom the drug was dispensed
- the date(s) and quantity of the drug dispensed to the participant.

The date and time of dose preparation and release will be maintained to support administration of study drug. The pharmacy will dispense the study medication and the clinical site staff will administer the study medication only to participants included in this study following the procedures set out in the study protocol. Study drug administration will be documented on the CRFs and/or other study drug accountability record. The inventory must be available for inspection by the CRA during the study. Drug supplies, excluding partially used or empty

containers, will either be collected at the end of the study by the CRA or returned by the PI or designee to Arrowhead Pharmaceuticals Inc. or the designated Arrowhead approved depot.

